### Statistical methods:

The study hypothesis is that short-term therapy with sacubitril/valsartan added on standard HF therapy improves cardiac efficiency in patients with systolic HF. Analysis of covariance (ANCOVA) will be used for statistical analysis, when appropriate. Other statistical analyses may also be implemented, as described in the statistical analysis plan (SAP).

Efficacy: The difference in the primary (cardiac efficiency) and exploratory efficacy parameters will be evaluated by comparing change from baseline at visit 3 between treatment groups. Change from baseline will be analysed using an ANCOVA, adjusting for treatment, strata, and baseline. From this model the treatment difference will be estimated with a 95% confidence interval (CI). In addition, treatment by stratification interaction analyses will be performed for the primary efficacy parameters in order to estimate within stratification group differences.

Safety: AEs reported during the study will be classified by system organ class (SOC) and preferred terms (PT) using the MedDRA coding system. The number and proportion (%) of subjects' AEs will be presented by treatment and dose level and the severity and causality will be tabulated with subject and event counts. Systolic and diastolic BP and HR and laboratory safety variables and their changes from the baseline values will be evaluated and summarized using descriptive statistics by treatment and dose level. The laboratory values tabulated as low, normal or high according to their reference ranges and clinically significant laboratory abnormalities will be listed.

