### **Primary Endpoint**

The primary endpoint, change from baseline in cardiac efficiency after 6 weeks on stable sacubitril/valsartan or valsartan therapy, will be analyzed by an ANCOVA including treatment and stratification as independent factors and covariate adjustment for baseline cardiac efficiency. From this model, the within treatment group (sacubitril/valsartan-valsartan) changes will be estimated by least square means and the corresponding treatment difference between treatments will be calculated with a 95% confidence interval and p-value. In addition, treatment by stratification interaction analyses will be performed for the primary efficacy parameters in order to estimate within stratification group differences. For both the baseline visit and visit 3, the results will be also summarized using descriptive statistics, with the visit 3 results to be summarized also by dose level and treatment arm.

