# Exploratory Endpoints

The changes in the following cardiac and systemic hemodynamics parameters will be evaluated as exploratory efficacy endpoints: EF, NT-proBNP, systemic BP, SVR, coronary vascular resistance and cardiac oxygen consumption. The change from baseline in these parameters after 6 weeks on stable sacubitril/valsartan or valsartan therapy will be analyzed by an ANCOVA including treatment and stratification as independent factors and covariate adjustment for baseline cardiac efficiency. From this model, the within treatment group (sacubitril/valsartan-valsartan) changes will be estimated by least square means and the corresponding treatment difference between treatments will be calculated with a 95% confidence interval and p-value. For both the baseline visit and visit 3, the results will be also summarized using descriptive statistics, with the visit 3 results to be summarized also by dose level and treatment arm.

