# 2.5.2 Statistical hypothesis, model, and method of analysis

The change from baseline in these parameters after 6 weeks on stable sacubitril/valsartan or valsartan therapy will be analyzed by an ANCOVA including treatment and stratification as

| Novartis | Confidential | Page 18 of 30          |
|----------|--------------|------------------------|
| SAP      |              | Study No. CLCZ696BFI03 |

independent factors and covariate adjustment for baseline cardiac efficiency. From this model, the within treatment group changes will be estimated by least square means and the corresponding treatment difference (sacubitril/valsartan-valsartan) will be calculated with a 95% confidence interval and p-value.

Descriptive statistics will be provided for these secondary endpoints by treatment arm including levels at each visit and change from baseline.

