# 2.10 Biomarkers

Biomarkers will be measured to understand the potential mechanisms of how sacubitril/valsartan changes myocardial efficiency. Blood samples will be obtained for measurement of NT-proBNP hs-troponin and creatinine to assess effects of interventions on hemodynamics before randomization and repeatedly on visit 3, after 6 weeks of stable sacubitril/valsartan or valsartan treatment.

These biomarkers will be summarized using descriptive statistics including levels at baseline and Visit 3, and change from baseline at Visit 3. Creatinine is collected as a safety laboratory parameter at all visits as described in Section 2.6.3, and will thus be summarized as part of safety laboratory. In addition NT-proBNP will be analysed by an ANCOVA according to description under secondary endpoints (Section 2.5.1). A shift table corresponding to those for safety lab will be provided.

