# 4 Change to protocol specified analyses

An additional parameter, viable myocardium energetic efficiency, is added as a sensitivity analysis for the primary endpoint as described in section 2.4.5.

In the protocol it was stated that all summary statistics will be done by dose level. Split of summary statistics by dose level, ie stratification factor, will be limited to the subject disposition, primary endpoint and overview of TEAEs.

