#### 1.1 Amendment(s) of the SAP

As SAP states: analyses for Viable myocardium energetic efficiency will be done using the same approach as is applied for the primary endpoint. For this reason, a summary statistic by strata and an ANCOVA model is added, where the treatment by strata interaction will be evaluated. Based on this model, the within stratum treatment difference will be estimated.

Regarding secondary endpoints. The SAP did not include ANCOVA models for the following parameters:

- Resting perfusion (PET)
- Viable myocardium resting perfusion (PET)
- Viable myocardium clearance rate (PET)
- Left ventricle mass (Echocardiography)
- Stroke volume (Echocardiography)
- Cardiac output (Echocardiography)
- Left ventricular mechanical work (SBP echocardiography x SV x HR)/ LV mass (Echocardiography)
- Global Longitudinal Strain (Echocardiography)
- Left ventricular systolic volume (Echocardiography)
- Left ventricular diastolic volume (Echocardiography)

Additional ANCOVA models will be added according to description under secondary endpoints: The change from baseline in these parameters after 6 weeks on stable sacubitril/valsartan or valsartan therapy will be analyzed by an ANCOVA including treatment and stratification as independent factors and covariate adjustment for baseline. From this model, the within treatment group changes will be estimated by least square means and the corresponding treatment difference (sacubitril/valsartan-valsartan) will be calculated with a 95% confidence interval and p-value.

SAP addendum Version: 1.0 Date: 04/07/2022 Sponsor: Novartis Finland Oy Study Code: CLCZ696BFI03 NCT No.: 2017-002113-64

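### The six exploratory ANCOVAs adjust for baseline cardiac efficiency instead of each endpoint's own baseline, and the documents do not agree on the covariate

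*SAP*

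**What the plan says.** Protocol 9.2.6 (Primary Endpoint) analyses change in cardiac efficiency by an "ANCOVA including treatment and stratification as independent factors and covariate adjustment for baseline cardiac efficiency". Here the covariate is the endpoint's own baseline. The next part of 9.2.6 (Exploratory Endpoints) states that change in EF, NT-proBNP, systemic BP, SVR, coronary vascular resistance and cardiac oxygen consumption "will be analyzed by an ANCOVA including treatment and stratification as independent factors and covariate adjustment for baseline cardiac efficiency". SAP 2.5.2 repeats this for the same six endpoints, with treatment and stratification as "independent factors and covariate adjustment for baseline cardiac efficiency". SAP 2.10 refers NT-proBNP back to the secondary-endpoint description.

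Two other places are worded differently:

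- The protocol synopsis (Statistical methods) treats primary and exploratory parameters together: "Change from baseline will be analysed using an ANCOVA, adjusting for treatment, strata, and baseline".
- The SAP addendum, section 1.1, adds ten PET and echocardiography parameters: "Additional ANCOVA models will be added according to description under secondary endpoints". It then describes an "ANCOVA including treatment and stratification as independent factors and covariate adjustment for baseline. From this model" the least squares means and the treatment difference are obtained. The words *cardiac efficiency* are gone.

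**The concern.** In an ANCOVA of change, the usual covariate is the baseline of the variable analysed. It removes the part of a chance baseline difference that returns as regression to the mean, and it reduces residual variance. Baseline efficiency does this for efficiency. For NT-proBNP or EF it does so only as far as it correlates with that endpoint's own baseline.

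The ANCOVA clause for the six endpoints is identical to the primary one, which suggests that it was carried over. Neither document explains the choice.

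Two things are at stake. First, the six endpoints make up the exploratory objective and provide the mechanistic reading of the primary result, each with a 95% confidence interval and p-value. At about 27 subjects per arm, avoidable loss of precision matters. Second, two programmers could follow these documents and fit different models to the same endpoint. If *baseline* in the addendum means the own baseline, closely related quantities get different models in one results section: k_mono and viable-myocardium clearance rate; SVR, defined as SBP/(SV x HR), and stroke volume or cardiac output; EF and the LV volumes.

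**Working it through.** **The wording side by side**

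| Place | Endpoints | Baseline covariate |
|---|---|---|
| Protocol 9.2.6, SAP 2.4.2 | primary | cardiac efficiency (own baseline) |
| Protocol 9.2.6, SAP 2.5.2 | six exploratory | cardiac efficiency |
| Protocol synopsis | primary and exploratory | *baseline* |
| SAP addendum 1.1 | ten added parameters | *baseline* |

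Two SAP passages favour reading plain *baseline* as the analysed variable's own value. Section 2.1.1 defines baseline as the last non-missing assessment before the first randomised dose, for data from which a change is derived. Section 2.4.4 uses the bare word for the own-baseline covariate of the primary model.

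**The plan's sample size, for context.** With a 15% difference, CV 19.7%, two-sided alpha 0.05 and 80% power, the normal approximation gives 2 x [19.7 x (1.960 + 0.842)/15]^2 = 27.08 per arm, against the stated 27. This concerns the primary endpoint and does not depend on the covariate issue. It supplies the 27 per arm (54 in total) used below.

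**Effect of the covariate.** The documents give no correlations, so these are assumptions:

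- The endpoint has baseline B and visit 3 value Y, each with variance 1, and corr(B, Y) = rho, taken as 0.5 to 0.9.
- Baseline efficiency W has corr(B, W) = r, taken as 0 to 0.7.
- W is related to Y only through B.

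Residual variance of the change:

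- adjusting for own baseline: 1 - rho^2
- adjusting for baseline efficiency: Var(Y - B) = 2(1 - rho) and Cov(Y - B, W) = -(1 - rho)r, which gives 2(1 - rho) - (1 - rho)^2 r^2
- ratio: [2 - (1 - rho)r^2]/(1 + rho)

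A baseline imbalance of one SD leaves an expected shift of (1 - rho)(1 - r^2) SD in the efficiency-adjusted difference. With own-baseline adjustment it leaves none. A typical imbalance of one standard error is sqrt(2/27) = 0.27 SD.

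| rho | r | Variance ratio | SE ratio | 54/ratio | Shift per SD of imbalance | Shift at 0.27 SD |
|---|---|---|---|---|---|---|
| 0.5 | 0 | 1.33 | 1.15 | 40.5 | 0.50 | 0.14 |
| 0.5 | 0.7 | 1.17 | 1.08 | 46.2 | 0.26 | 0.07 |
| 0.7 | 0 | 1.18 | 1.08 | 45.9 | 0.30 | 0.08 |
| 0.7 | 0.5 | 1.13 | 1.06 | 47.7 | 0.23 | 0.06 |
| 0.9 | 0 | 1.05 | 1.03 | 51.3 | 0.10 | 0.03 |
| 0.9 | 0.7 | 1.03 | 1.01 | 52.6 | 0.05 | 0.01 |

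Example (rho 0.5, r 0.7): (2 - 0.5 x 0.49)/1.5 = 1.755/1.5 = 1.17.

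Blood pressure, SVR, coronary resistance and k_mono share components with efficiency, so |r| may be higher for them. At |r| = 0.9 the ratio is (2 - 0.5 x 0.81)/1.5 = 1.06 for rho 0.5 and (2 - 0.1 x 0.81)/1.9 = 1.01 for rho 0.9.

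**Simulation under the same assumptions** (8,000 trials per case, 27 per arm, three binary strata factors in the model). Variance ratios were 1.32, 1.17, 1.18, 1.12, 1.04 and 1.02 in the order of the table. Mean bias was at most 0.004 SD for either covariate. Type I error was 4.5% to 5.3% with baseline efficiency and 4.9% to 5.1% with own baseline.

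**The case against.** The strongest reply is that the protocol body and the SAP agree: both prespecify baseline efficiency, and the model is valid. A change score already subtracts the own baseline, so under randomisation either covariate estimates the same treatment difference. All of this stands. It means that the related parameters listed above would differ in precision and in conditional imbalance, not in what they estimate. It also means that SAP section 4, which lists departures from the protocol, had nothing to list here; its silence is no evidence either way.

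Second, bare *baseline* is ambiguous. The synopsis is a summary, and the addendum governs the ten added parameters and claims to follow the secondary-endpoint description, so it could be read as importing baseline efficiency. That is possible, but SAP 2.1.1 and 2.4.4 point the other way, and an ambiguity in the covariate of 16 reported models is itself worth removing.

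Third, the size rests on assumed correlations, equal variances at the two visits, and efficiency having no prognostic value beyond the endpoint's own baseline. The simulation shares these assumptions, so it checks the algebra and not the assumptions. If efficiency does carry independent information, the loss is smaller. The 33% figure is the worst corner of the range; the other tabulated cases give 3% to 18%.

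Finally, the six endpoints are exploratory and the trial was not powered for them. That limits the weight of the point but does not supply a reason for the covariate.

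**Conclusion.** The point holds. Protocol 9.2.6 and SAP 2.5.2 adjust six exploratory endpoints for the baseline of a different variable, without a stated reason. The synopsis and the addendum use wording that most naturally means the endpoint's own baseline. That the clause was carried over from the primary model is an inference, though a likely one.

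The consequence is modest. There is no bias over randomisation, no inflation of type I error and no effect on the primary analysis. On the assumed correlations, residual variance is 3% to 33% larger and standard errors 1% to 15% larger, equivalent to using about 40 to 53 of 54 subjects. A typical chance imbalance leaves a shift of 0.01 to 0.14 SD. These ranges are illustrative. For endpoints highly correlated with efficiency the variance loss may be only 1% to 6%. The point should be fixed because the repair is free and settles which model is to be run.

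**What to change.** In SAP 2.5.2, replace baseline cardiac efficiency with the baseline value of the endpoint being analysed. Use the same words in addendum section 1.1, so that all six endpoints and the ten added parameters follow one model. Align Protocol 9.2.6, or record the clarification in SAP section 4; Protocol 9.2.1 leaves the technical details of the analysis to the SAP. If baseline efficiency was intended, add a sentence saying why, and state in the addendum which baseline is meant. If results were already unblinded when the change is made, date it and report both versions.

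The cost is one phrase in the SAP and one in the addendum, and one variable name per model. The own baselines are already collected at the baseline visit, so no new data are needed and the primary analysis does not change.

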# 2.5.3 Handling of intercurrent events

The secondary endpoints are considered exploratory. In general, all available data in applicable analysis set will be used for the analyses of secondary endpoints, irrespective of if any intercurrent events have occurred.

# 2.5.4 Handling of missing values not related to intercurrent event

No imputations will be done for any missing data related to secondary endpoints as these are considered exploratory.

# 2.5.5 Sensitivity analyses

No sensitivity analysis will be conducted for secondary endpoints.

# 2.5.6 Supplementary analyses

In addition to the secondary endpoints stated above, a number of additional parameters related to the PET and Echocardiography will be collected (see DTS). All of these parameters will be summarized using descriptive statistics including levels by visit and the corresponding changes from baseline.

# 2.6 Safety analyses

Analyses of all safety endpoints will be based on the Safety set.

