### 5.9 Information to be collected on screening failures

From subjects screened but not included in the study, the following data will be collected on CRFs: date of IC, demography (year of birth, sex and race), the inclusion/exclusion criterion/criteria causing the exclusion and the date of the decision of exclusion.

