For the screening/run-in period, valsartan will be taken from local commercial stock and subsequently labelled as a research drug by Tamro. During the screening/runin period, valsartan can be dispensed by any member of the study team. For the treatment period, valsartan is manufactured by Novartis in accordance with GMP guidelines. The labelling will be also done in compliance with GMP regulations after which the study drug will be released at Novartis. Valsartan will be stored in the Heart Center in locked cabinets according to instructions provided in the SPC. The subjects will receive their study treatment according to the randomization list which contains randomization numbers and allocated treatments. During the treatment period, the study drugs will be dispensed by an unblinded member of the study team and the subjects will take the study drugs and corresponding matching placebo tablets at home BID. After the randomization, 50% of the subjects will continue in the valsartan treatment arm, on a starting dose of 80 mg BID or 160 mg BID if they were on this dose during the screening/run-in (see Figure 3). There is one visit scheduled for possible up-titration of the dose (visit 1) and during this visit every subject should be attempted to be up-titrated to the next dose level (sacubitril/valsartan 200 mg or valsartan 160 mg, if the latter needed), if clinically possible. If up-titration is not clinically possible, the starting dose should be maintained. During the treatment period, subjects will receive new study drug packages (active drug and placebo) from the unblinded drug dispenser, as applicable.

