During the screening/run-in period, the subjects will receive valsartan treatment that will replace their previous ACEI or ARB HF therapy. Valsartan during the screening/run-in period may be dispensed by any member of the study team. The screening/run-in dose of valsartan (80 mg BID or 160 mg BID) will be decided by the investigator based on the subject's clinical status, prior HF therapy and concomitant medications. The subjects will have a scheduled safety and efficacy assessment visit during the screening/run-in period (screening visit 2 in the study schedule, Table 3). If deemed sufficient by the investigator, screening visit 2 can be performed remotely. If so, safety blood sampling, eligibility criteria review, adverse events and concomitant medication must be assessed.

Dose reduction of a loop diuretic is allowed during the screening/run-in to prevent hypotension. Unscheduled visits may be performed at any time during the screening/run-in period. Study visit should be performed as close proximity to the stated day in the study schedule (Table 3) as possible.

The subject has to tolerate at the minimum 80 mg BID valsartan at a stable dose for minimum of 4 weeks in order to be eligible for the treatment period. Before the PET-scan, a urine pregnancy test should be performed for female subjects of childbearing potential. During the baseline visit, PET-scan and echocardiography will be done and blood samples for biomarker assessment will be drawn. After all other study procedures are performed at the baseline visit and the subject is deemed eligible for the study, he/she will be randomized and start the double-blinded treatment period.

The results for the laboratory tests taken during the on-site screening visits do not need to be available before decision-making (i.e. starting valsartan treatment), but they have to be reviewed as soon as possible after they become available in order to ensure subject safety. All screening/run-in period laboratory results must be available and reviewed before randomization, except the results of the laboratory tests taken on the baseline visit, as randomization is performed on the same day as the baseline visit.

Adverse events and changes in concomitant medications will be recorded throughout the screening/run-in period.

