# 9.2.3 Data sets to be analyzed

The following analysis sets will be used for the statistical analysis and presentation of data:

- **The safety set** will consist of all randomised subjects who received at least one dose of the study medication in the treatment period, provided that there was at least one safety follow-up performed for the subject.
- The full analysis set (FAS) will consist of all randomised subjects who have received at least one dose of study medication in the treatment period and have at least one post-baseline assessment of any efficacy endpoints.
- **The per protocol set (PPS)** will consist of all subjects in the FAS who received at least 75% of the study drug doses, and do not have any other major protocol violations which will affect the assessment of efficacy. Major/important protocol violations may include, but are not limited to, the following:
  - Non-fulfillment of all inclusion criteria
  - o Fulfillment of at least one exclusion criteria
  - Use of certain concomitant medications (this will be judged on a case to case basis, depending on extent of treatment)

The final criteria for PPS, regarding which protocol deviations that warrant exclusions, will be determined when all data on protocol violations/deviations are available and before breaking the blind. The FAS is considered as the primary analysis dataset, and will be used for all primary and secondary efficacy analyses. The primary efficacy analysis will be repeated using the PPS. Any significant discrepancy between the results from the FAS and the PPS will be analysed and discussed.

Baseline presentations will be based on the safety set.

Safety presentations will be based on the safety set

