### 9.2.7 Analysis of safety variables

### 9.2.7.1 Evaluation of adverse events

AEs reported during the study will be classified by system organ class (SOC) and preferred terms (PT) using the MedDRA coding system. AEs will be displayed in a frequency table by dose level and treatment arm. The number and proportion (%) of subjects having each AE will be tabulated by SOC and PT and dose level. Severity of the AEs (mild, moderate, severe) and causality to the study treatment will be

tabulated with subject and event counts. SAEs and other significant AEs will be evaluated case by case.

AEs occurring before and after the initiation of the double-blind treatment period will be reported separately.

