# 2.2 Analysis sets

The following analysis sets will be used for the statistical analysis and presentation of data:

- The safety analysis set (SAF) will consist of all randomised subjects who received at least one dose of the study medication in the treatment period, provided that there was at least one safety follow-up performed for the subject.
- The full analysis set (FAS) will consist of all randomised subjects who have received at least one dose of study medication in the treatment period and have at least one post-baseline assessment of any efficacy endpoints.
- The per protocol set (PPS) will consist of all subjects in the FAS who received at least 75% of the study drug doses, and do not have any other major protocol violations which will affect the assessment of efficacy. Major/important protocol violations may include, but are not limited to, the following:
  - Non-fulfillment of all inclusion criteria
  - o Fulfillment of at least one exclusion criteria
  - Use of certain concomitant medications (this will be judged on a case to case basis, depending on extent of treatment)

The final criteria for PPS, regarding which protocol deviations that warrant exclusions, will be determined when all data on protocol violations/deviations are available and before breaking the blind. The decision of what protocol violations/deviations will lead to exclusion as well as the final classification of subjects according to analysis sets will be documented and signed off before breaking the blind. These decisions will be documented in a separate Pre-Analysis Review document.

The FAS is considered as the primary analysis dataset, and will be used for all primary and secondary efficacy analyses. The primary efficacy analysis will be repeated using the PPS.

| Novartis | Confidential | Page 13 of 30          |
|----------|--------------|------------------------|
| SAP      |              | Study No. CLCZ696BFI03 |

Any significant discrepancy between the results from the FAS and the PPS will be analysed and discussed.

Baseline presentations will be based on the safety set.

Safety presentations will be based on the safety set.

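### No planned study-report safety output clearly covers subjects who took run-in valsartan but were not randomised, so the run-in safety summaries tend to look too favourable

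*SAP*

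**What the plan says.** **Run-in exposure.** Valsartan replaces each subject's own ACE inhibitor or ARB at screening visit 1. Under protocol 6.2 the run-in "valsartan will be taken from local commercial stock and subsequently labelled as a research drug". Inclusion criterion 7 requires at least 4 weeks of tolerated treatment, and protocol 7.1 enters a subject into the study only at randomisation.

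**Run-in data.** Protocol 7.1: "Adverse events and changes in concomitant medications will be recorded throughout the screening/run-in period". Protocol 8.3.4 counts adverse events from consent. Potassium, creatinine and haemoglobin are measured at both screening visits (protocol 8.1.2).

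**Promised run-in outputs.** Protocol 9.2.7.1: "AEs occurring before and after the initiation of the double-blind treatment period will be reported separately". SAP 2.6.1 plans a separate listing of run-in events. Protocol 9.2.7.2 and 9.2.7.3 and SAP 2.6.3 and 2.6.4.1 plan run-in changes from screening visit 1 in laboratory values, blood pressure and heart rate.

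**Population rule.** SAP 2.6: "Analyses of all safety endpoints will be based on the Safety set". SAP 2.2: the safety set "will consist of all randomised subjects who received at least one dose of the study medication in the treatment period", with at least one safety follow-up. Protocol 9.2.3: "Safety presentations will be based on the safety set". No wider set is defined in either document or in the SAP addendum.

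**Subjects who are not included.** Protocol 5.9: "From subjects screened but not included in the study, the following data will be collected on CRFs: date of IC, demography", followed by the criterion that caused exclusion and the date of that decision. It lists no adverse event, laboratory or vital-sign data.

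**The concern.** The safety set suits the double-blind comparison, but it is also the only set available for the run-in outputs, and getting into it depends partly on how the run-in went. Exclusion criteria 6 to 9 remove subjects with symptomatic hypotension, low eGFR, high potassium or high creatinine that persists during the run-in, and inclusion criterion 7 removes those who do not tolerate valsartan. Subjects with run-in harm are therefore more likely than others to be missing from the tables and listings that describe the run-in.

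At stake is the description of what happened to people while they took a trial-supplied drug after consent. A study report that follows the SAP could present run-in potassium, creatinine and blood pressure changes as the run-in experience without saying that those who failed the run-in are not in them.

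**Working it through.** The plan gives no figure on this point. The check is to follow the population rule through the outputs and then to illustrate the size under stated assumptions.

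**Step 1: who is in the set.** SAP 2.2 requires randomisation and a treatment-period dose. A run-in failure has neither, so the number of unrandomised subjects in the safety set is zero by definition.

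**Step 2: where a run-in failure could appear.**

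| Output | Population named | Covers run-in failures? |
|---|---|---|
| AE tables (SAP 2.6.1) | Safety set; events on or after randomisation | No |
| Separate run-in AE listing (SAP 2.6.1) | None of its own; SAP 2.6 governs | Not as written |
| SAE and death listings (SAP 2.6.2, 5.6) | Safety set | No |
| Run-in laboratory changes (SAP 2.6.3) | Safety set | No |
| Run-in BP and HR changes (SAP 2.6.4.1) | Safety set | No |
| Disposition counts, screening-failure listing (SAP 2.3.1) | Includes screened subjects | Yes, but not safety outputs |

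The AE listing format also presumes randomisation. SAP 2.6.1 counts relative day from the first dose of study drug, SAP 2.1.1 derives it from the baseline date, and SAP 5.6 heads the section by treatment. A run-in failure has no randomised treatment and may have no baseline date.

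**Step 3: number left out.** Inputs: 60 randomised (protocol 5.2), and *f*, the share of subjects taking run-in valsartan who are not randomised. *f* is not in the documents and is assumed here.

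Number left out = 60/(1 − *f*) − 60

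- *f* = 0.10: 66.7 − 60 = 6.7, about 7
- *f* = 0.20: 75.0 − 60 = 15
- *f* = 0.30: 85.7 − 60 = 25.7, about 26

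**Step 4: effect on a run-in rate.** Let *p* be the rate of some run-in abnormality in randomised subjects and *q* the rate in run-in failures. The safety-set output shows *p*. The rate among all exposed is (1 − *f*)*p* + *f q*, so the output is too low by *f*(*q* − *p*). With *p* = 5% and *q* = 50%, both assumed:

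- *f* = 0.10: 0.90 × 5% + 0.10 × 50% = 9.5%, against 5% shown
- *f* = 0.20: 0.80 × 5% + 0.20 × 50% = 14.0%, against 5% shown

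The direction needs only *q* > *p*, which exclusions 6 to 9 make likely for the measures they name. If *q* = *p*, there is no distortion.

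**The case against.** The case on the other side has real force.

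- **Serious events are reported.** A reader might infer that SAEs and deaths in run-in failures go unreported. The documents do not support that. Protocol 8.3.4.1.2 sends every SAE from consent to sponsor safety within 24 hours, protocol 8.3.4.6 sets up reconciliation, and protocol 10.6 reconciles the safety and study databases before closure. What is missing is a clear place in the study-report outputs.
- **Protocol 5.9 does not say that other data are discarded.** A reader might infer that it does. It lists items to collect without the word only, while protocol 7.1 and 8.3.4 require run-in events to be recorded and protocol 9.2.4 says that all collected data are listed. The sections are unaligned, which is weaker than a rule to delete.
- **The safety-set ticks in SAP 5.6 are not decisive.** Subject disposition is ticked for the safety set, although SAP 2.3.1 requires it to count screened subjects. The point therefore rests on the population sentences in SAP 2.6 and protocol 9.2.3. The separate run-in AE listing carries no limit of its own and could be programmed for everyone, but nothing says that it will be.
- **Abnormal values are not shut out entirely.** A reader might infer that the safety set can hold no subject whose run-in potassium stayed above 5.2 mmol/l. Protocol 7.1 lets randomisation go ahead before the baseline-visit results are known, so such a subject can be randomised. Abnormalities that resolve after concomitant medication is modified also stay in.
- **Not every run-in failure reflects harm.** Systolic pressure outside 110 to 160 mmHg at randomisation, for example, is also disqualifying. Subjects were already on a stable ACE inhibitor or ARB, which may keep failures few.

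All of this limits the claim. None of it supplies a population for the run-in laboratory and blood pressure changes other than the randomised safety set.

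**Conclusion.** The point holds in this limited form. Followed as written, the population rule leaves unrandomised subjects who took trial-supplied valsartan out of the run-in laboratory and blood pressure changes, and no planned study-report output clearly covers their adverse events, SAEs or deaths. The run-in summaries then describe only those who got through the run-in and tend to understate run-in harm.

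The size cannot be determined. The 7 to 26 subjects rest on assumed failure rates of 10% to 30%, and the distorted rates rest on two further assumptions. The direction rests on the safety-based exclusion criteria.

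The selection might be read as putting the trial's main result in doubt. It does not: the primary endpoint and the between-arm safety comparison use randomised subjects and are unaffected. The run-in outputs are descriptive and uncontrolled. This is worth correcting because it is cheap, not because the trial depends on it.

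**What to change.** 1. Add to SAP 2.2 a run-in set: all subjects who took at least one dose of trial-supplied run-in valsartan.
2. In SAP 2.6, name that set for the run-in AE listing, including SAEs and deaths, and for the run-in laboratory, blood pressure and heart rate changes from screening visit 1. Index these by day from the start of run-in valsartan, with randomised or not randomised shown in place of treatment arm.
3. Keep the present safety set for all double-blind outputs.
4. Align protocol 5.9 with 7.1 and 8.3.4, so that adverse event and laboratory data recorded in the run-in stay on the CRF for subjects who fail it.

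The cost is a few sentences and a few extra listings and summaries. No new assessments are needed, because the protocol already requires these data. If sites read 5.9 narrowly and did not enter them, they would have to be entered from source documents. If that cannot be done, the run-in tables should at least state that they cover randomised subjects only and give the number of run-in failures left out.
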